## **11.4.2 Prior and Concomitant Medications**

Prior and concomitant medications will be coded using the World Health Organization dictionary (WHO) Drug Dictionary (WHODD) latest version. Each medication will be assigned a Preferred Term (PT). Please refer to the Coding Convention document for further details on the coding of medications.

The number and percentage of subjects with prior and concomitant medication WHO Drug Dictionary PTs will be summarized by treatment group and overall for the Intention-to Treat Population [TFL Shell Table 14.1.4, 14.1.5].

[figure not shown]
All prior and concomitant medications and procedures will be listed [TFL Shell Listing 16.2.4.3, 16.2.4.4].

## 11.5 Safety Analyses

The primary safety endpoints are type, frequency, and intensity of AEs evaluated until the end of treatment and change from baseline in the parameters of physical and neurological examination, vital signs, MRI imaging, Electrocardiogram (ECG), routine hematology and biochemistry evaluation in blood and urine, evaluation of autoimmune antibodies in blood and inflammatory markers in blood and CSF. Other cognitive and clinical variables related to safety are provided in Section 5.3.5.1 and Section 5.3.5.3 of the study protocol. Continuous and categorical laboratory data will be summarized separately.

#### 11.5.1 Adverse Events

All adverse events (AEs) will be coded using the most up-to-date version of the MedDRA dictionary. As AEs are collected starting from the moment of the Informed Consent Form (ICF) signature, AEs and

treatment emergent adverse events (TEAEs) will be discriminated. Please refer to Section 8.8 for the definition of TEAEs.

An overview of AEs and TEAEs will be given in terms of the number and percentage of subjects and number of AEs and TEAEs per treatment group (and overall) for the Safety Population within each of the following categories:

- AEs
- TEAEs
- Serious AEs (SAEs)
- Serious TEAEs
- Severe adverse events
- Severe TEAEs
- Adverse drug reactions
- Serious adverse drug reactions
- AEs leading to discontinuation of study treatment
- AEs leading to discontinuation from the study
- TEAEs leading to discontinuation from the study
- AEs with an outcome of death
- TEAEs with an outcome of death

[TFL Shell Table 14.3.2.1]

Selected TEAE categories from above will also be summarized by MedDRA SOC and PT [TFL Shell Table 14.3.2.2, 14.3.2.3, 14.3.2.4, 14.3.2.5, 14.3.2.6, 14.3.2.7, 14.3.2.8], according to severity (mild, moderate, severe) [TFL Shell Table 14.3.2.9] and according to relationship to drug [TFL Shell Table 14.3.2.10].

[figure not shown]
Most frequent TEAEs will be presented by Treatment Group in a Table [TFL Shell Table 14.3.2.11] and a bar chart [TFL Shell Figure 14.3.1], where most frequent TEAEs are defined events which occur in at least 10% of subjects in any treatment group. Time to first SAE since first injection (in days) will be presented graphically as a bar chart per cohort with subjects as individual points [TFL Shell Figure 14.3.2].

All AEs [Non-Injection Site Reactions (ISR) and ISRs] will be listed [TFL Shell Listing 16.2.7.1 to 16.2.7.6.3].

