1.1.2.3 Clinical Data

ACI-35.030

At the time of the version of this protocol, 26 subjects have been exposed to ACI-35.030, i.e. the second generation vaccine, or placebo in the current study, in sub-cohorts 1.1, 1.2 and 1.3.

ACI-35

Although ACI-35 differs from the currently tested vaccine, ACI-35.030, in its composition and adjuvants, the safety data generated in the Phase Ib study are included below for information.

The safety, tolerability and immunogenicity of ACI-35 vaccine was evaluated in a clinical phase Ib study conducted in subjects with mild to moderate AD in UK and Finland (ACI-35-1201: A Phase Ib Multicenter, Double-Blind, Randomized, Placebo-Controlled Study of the Safety, Tolerability and Immunogenicity of ACI-35 in Subjects with Mild to Moderate Alzheimer's Disease). The clinical trial was completed on 15 June 2017.

Five cohorts were studied. Each cohort consisted of a different dose ($300 \mu g$, $900 \mu g$ or $1800 \mu g$) and/or dosing regimen spread over 24 weeks of varying intervals (2, 3 or 5 dose administrations), followed by a final injection that occurred at Week 48 (cohorts 2-5) or between Week 48 and Week 76 (cohort 1).

Twenty-four subjects were randomized and received at least 1 dose of study vaccine. Twentytwo completed the study. Two subjects discontinued the study due to a significant unrelated medical condition which seriously hampered or made the completion of the study impossible.

Overall, ACI-35 was well tolerated in the participating population at all doses tested. Injection site erythema and injection site reactions and fatigue were the most common study vaccine-related Treatment Emergent Adverse Events (TEAE). There was no evidence clinically or from laboratory or radiology findings to suggest the development of CNS inflammation. In general, no pattern of AEs emerged, except injection site reactions on active treatment, which occurred in all subjects at the highest doses tested but were generally mild and self-limiting and did not lead to subject withdrawal.

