1.1.5 Conclusion

The preceding clinical study ACI-35-1201 demonstrated that ACI-35, i.e. the first generation vaccine, was safe and well tolerated at all doses and treatment regimens tested. However, the IgG response induced in individuals after the first injection did not result in a boosting effect upon subsequent injections and thus, considered of an insufficient magnitude to confer a sustainable clinical benefit. To address this situation, second generation vaccines were developed. ACI-35.030 utilizes properties of ACI-35 (i.e. the liposome and antigen composition). JACI-35.054 incorporates the same pTau peptide antigen, but presents the pTau to the immune system in a different way. In JACI-35.054 the pTau peptide is attached to a large carrier protein (CRM197) instead of being inserted in a liposome. The carrier protein should help the immune system to respond more efficiently to the pTau peptide. At the time of the version of this protocol, ACI-35.030 and JACI-35.054 have been well tolerated in humans in this ongoing clinical study. A total of four serious adverse events in four different subjects have been reported to date (at the time of the version of this protocol) in cohort 1, all considered unlikely related to the study medication.

The strong rationale for testing compounds which have the potential to modify Tau pathology in AD, in conjunction with favorable preclinical safety and efficacy profile, make ACI-35.030 and JACI-35.054 suitable candidates for testing in AD subjects.

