5.3.5.2 Adverse Events

All adverse events (AEs) will be coded using the most up-to-date version of the Medical Dictionary for Regulatory Affairs (MedDRA). As AEs are collected starting from the moment of the ICF signature, AEs and treatment-emergent adverse events (TEAEs) will be discriminated. A TEAE is defined as any AE that has an onset date/time on or after the first dose of investigational product, or any pre-existing condition that has worsened on or after the first dose of investigational product.

Overview of AEs will be given in terms of number and percentage of subjects per dose group experiencing:

- o AEs
- o SAEs
- Severe adverse events
- Adverse drug reactions
- AEs leading to withdrawal
- o Deaths

AEs will also be summarized by System Organ Class and Preferred Term, according to severity (mild, moderate, severe) and according to relationship to drug.

Most frequent AEs will be presented per dose group in bar charts and time to first SAE will be presented graphically.

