Figure 14.2.6 Mean Time Course of Change from Baseline AD Biomarkers (in CSF) by Treatment Group (Intention-to-Treat Population)			Х
Figure 14.2.7 Individual Change from Baseline over Time of AD Biomarkers (in Plasma) Intention-to-Treat Population)			Х
Figure 14.2.8 Individual Change from Baseline over Time of AD Biomarkers (in CSF) (Intention-to-Treat Population)			Х
Figure 14.2.9 Box Plot of the Actual Values of AD biomarkers (in Plasma) by Visit and Treatment Group (Intention-to-Treat Population)			Х
Figure 14.2.10 Box Plot of the Actual Values of AD biomarkers (in CSF) by Visit and Treatment Group (Intention-to-Treat Population)			Х
Figure 14.2.11 Box Plot of the Actual Log10-Transformed Values of AD biomarkers (in Plasma) by Visit and Treatment Group (Intention-to- Treat Population)			х
Figure 14.2.12 Box Plot of the Actual Log10-Transformed Values of AD biomarkers (in CSF) by Visit and Treatment Group (Intention-to- Treat Population)			Х
Figure 14.2.13 Box Plot of the Fold-change from Baseline Values of AD biomarkers (in Plasma) by Visit and Treatment Group (Intention- to-Treat Population)			X
Figure 14.2.14 Box Plot of the Fold-change from Baseline Values of AD biomarkers (in CSF) by Visit and Treatment Group (Intention-to- Treat Population)			х
Figure 14.2.15 Box Plot of the Change from Baseline of the Log10-Transformed Values of AD biomarkers (in Plasma) by Visit and Treatment Group (Intention-to-Treat Population)			х
Figure 14.2.16 Box Plot of the Change from Baseline of the Log10-Transformed Values of AD biomarkers (in CSF) by Visit and Treatment Group (Intention-to-Treat Population)			х
Figure 14.3.1 Bar Chart of Most Frequent Treatment-Emergent Adverse Events (Safety Population)			Х
Figure 14.3.2 Bar Chart of Time to first SAE (in days) by Cohort with Individual Points (Safety Population)			Х
Figure 14.4.1 Box Plot of Hematology by Visit and Treatment Group (Intention-to-Treat Population)			Х
Figure 14.4.2 Box Plot of Biochemistry by Visit and Treatment Group (Intention-to-Treat Population)			Х

Statistical Analysis Plan

[figure not shown]
MAIN Statistical Analysis Plan	Cohort 1 Interim Analysis (IA1)	Cohort 1 IA2 to IA7 Cohort 2 IA1 to IA6	Final Analysis
Figure 14.5.1 Box Plot of Vital Signs by Visit and Treatment Group (Intention-to-Treat Population)			Х
Figure 14.5.2 MRI Volume Mean Change from Baseline by Brain Region by Treatment Group and Visit (Intention-to-Treat Population)			Х

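### The one planned time-to-first-SAE figure is grouped by cohort, so as worded it pools active doses with placebo, and the SAP does not say how subjects without an SAE are shown

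*SAP*

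**What the plan says.** Protocol section 5.3.5.2 asks only for a graph: "time to first SAE will be presented graphically". It fixes no grouping, plot type or censoring rule.

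SAP section 11.5.1 supplies the form. Time to first SAE since first injection, in days, is to be "presented graphically as a bar chart per cohort with subjects as individual points". Appendix 2 lists it as "Figure 14.3.2 Bar Chart of Time to first SAE (in days) by Cohort with Individual Points (Safety Population") and marks it for the final analysis only. Neither place mentions treatment group, placebo, censoring or numbers at risk.

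The surrounding text is organised differently. Section 11.0 makes treatment group the default for descriptive summaries and adds main-cohort totals where applicable. Its bracketed list of groups names the five active doses but not placebo, although sections 9.0 and 9.4 refer to a placebo arm. In 11.5.1, the bar chart of most frequent TEAEs (Figure 14.3.1) is by treatment group. For SAE incidence the same section says: "An overview of AEs and TEAEs will be given in terms of the number and percentage of subjects", and the grouping is "per treatment group (and overall) for the Safety Population within each of the following categories". Those categories include SAEs and serious TEAEs (Table 14.3.2.1). Table 14.3.2.3 gives serious TEAEs by MedDRA term, and Listing 16.2.7.2 gives them by subject.

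**The concern.** Safety is a primary objective, and randomisation to vaccine or placebo takes place within each sub-cohort. A graph of time to first SAE is useful if it shows whether SAEs come earlier or later on vaccine than on placebo, or cluster after injections, given how long each subject was followed. A graph grouped by cohort removes the arm from the picture. A graph with no stated place for SAE-free subjects removes the follow-up. No other planned output shows SAE timing in a way that allows for follow-up: the tables give counts and percentages, and the listing covers only subjects with events. The loss is therefore SAE timing by arm, not SAE incidence by arm.

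**Working it through.** **Plan's own figures.** The plan gives no number for time to first SAE. Its nearest safety-precision statement (Protocol 5.3.1, SAP 6.1) reproduces:
- Chance of at least one event in 6 subjects: 1 − 0.99^6 = 5.85% (stated 6%) and 1 − 0.90^6 = 46.9% (stated 47%).
- Upper bound with 0 of 6: 1 − 0.20^(1/6) = 23.5% (stated 24%) and 1 − 0.10^(1/6) = 31.9% (stated 32%).

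The plan thus describes safety at this size and does not test it.

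**Step 1: what one cohort group contains.** SAP 6.0 says sub-cohort 2.3 and Cohort 3 were not started. By main cohort, Cohort 1 combines 300, 900 and 1800 µg with placebo (four groups in one), and Cohort 2 combines 15 and 60 µg with placebo (three in one). If cohort means sub-cohort, doses stay apart, but active and placebo still share a group, because each sub-cohort is planned as 6 active and 2 placebo. Under either reading the stated grouping does not separate the arms.

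**Step 2: what pooling hides (illustration, assumed risks).** At 3:1 allocation the cohort risk is 0.75 × p(active) + 0.25 × p(placebo).
- 10% and 10%: 0.75 × 10 + 0.25 × 10 = 10%.
- 13.3% and 0%: 0.75 × 13.3 + 0.25 × 0 = 10%.

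The cohort view is the same for no difference and for all SAEs on vaccine. The treatment-group columns of Table 14.3.2.1 would separate the two cases.

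**Step 3: why SAE-free subjects need a stated place (conditional illustration).** Suppose the bars were mean days among subjects with an SAE. The SAP does not say this. With a constant hazard over T = 74 weeks and risk r, λ = −ln(1 − r)/T, and the mean time among those with an event is 1/λ − T·e^(−λT)/(1 − e^(−λT)).

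| Risk by week 74 | Mean weeks to first SAE, among those with one |
|---|---|
| 5% | 36.7 |
| 20% | 35.6 |
| 40% | 33.9 |

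An eightfold rise in risk moves the mean by 36.7 − 33.9 = 2.8 weeks. Event times alone say little about risk, so the display needs the subjects without events and their follow-up.

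**Step 4: what a split by arm could do.** The plan gives no alpha, power or hazard ratio for SAEs. Assume two-sided 0.05, all active doses together against placebo at 3:1, and power = Φ(√(d × 0.75 × 0.25) × ln HR − 1.96), where d is the number of subjects with an SAE.

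| d | HR 2 | HR 3 | HR 5 |
|---|---|---|---|
| 4 | 9% | 16% | 29% |
| 12 | 18% | 38% | 68% |

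For 80% power, d would have to be about 88 (HR 2) or 35 (HR 3). Splitting by arm makes the figure readable; it does not make it a test.

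**The case against.** The case for leaving the figure alone has four parts.

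- **The comparison is planned elsewhere.** A reader might infer that the plan cannot show whether a vaccine dose raises SAE risk. The documents do not support that: Table 14.3.2.1 gives SAEs and serious TEAEs by treatment group, Table 14.3.2.3 and Listing 16.2.7.2 add detail, and the DSMB receives unblinded safety packages during the study. This stands in full and limits the point to one figure.
- **The content is partly unknown.** A reader might also infer that the figure uses only subjects who had an SAE and that bar height is their mean time. Neither is stated. The title says Safety Population, bar height is undefined, and the shell is in a separate document not among those reviewed. It could mark the arm on each point. This stands too. What remains is that the SAP as worded groups by cohort and leaves SAE-free subjects unaddressed.
- **Interim counts cannot size it.** Protocol 1.1.5 says "A total of four serious adverse events in four different subjects have been reported to date" in Cohort 1, all judged unlikely to be related. Section 1.1.2.3 says "26 subjects have been exposed to ACI-35.030" or placebo. It is tempting to turn these into a share of subjects missing from the figure, or a split by arm. But they are a snapshot at protocol version 7 for a figure produced only at the final analysis. Sub-cohort 1.2 reached 25 subjects, so Cohort 1 would be 8 + 25 + 8 = 41 if the other two stayed at 8 with no replacements. Final SAE counts, and the arms of those four subjects, are not given.
- **The SAP complies with the protocol, and events are few.** The protocol asks only for a graph, and Step 4 shows that formal comparison has little power. This argues against a test or an elaborate set of curves. It does not argue for a grouping that hides the arm, since a simpler plot by arm uses the same data.

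**Conclusion.** The point holds as a small improvement. As worded, Figure 14.3.2 combines active doses and placebo and gives no handling of subjects without an SAE, so this one descriptive figure cannot show SAE timing by randomised arm or account for follow-up. Its grouping also differs from the SAP's default of treatment group, without a stated reason. SAE incidence by treatment group is not lost, and no primary conclusion depends on the figure.

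The conclusion rests on the SAP text alone; a shell that already marks arm and shows SAE-free subjects would reduce it to a wording correction. The pooled-risk, mean-time and power numbers illustrate the mechanism under assumed risks, a constant hazard and 3:1 allocation. They are not estimates for this trial.

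**What to change.** In SAP 11.5.1 and Appendix 2, redefine Figure 14.3.2:

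- **Grouping:** by treatment group, with each active dose shown and placebo as a separate group. State whether placebo is pooled across sub-cohorts (Protocol 5.3.4 allows pooling for presentation), and add placebo to the group list in SAP 11.0.
- **Event:** first treatment-emergent SAE, timed from first injection. AEs are collected from consent, so the restriction keeps out events before dosing.
- **Form:** preferably a swimmer plot with one line per Safety Population subject, the event marked, and SAE-free subjects shown and censored at last contact. A cumulative-incidence plot with numbers at risk is an alternative.
- **Label:** descriptive, in view of the few events, with a reference to Tables 14.3.2.1 and 14.3.2.3 for incidence.

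The cost is a short SAP edit and reprogramming one figure, using data already collected.

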2.2 Study Endpoints

2.2.1 **Primary Endpoints**

Safety and tolerability: Adverse events, immediate and delayed reactogenicity (e.g. anaphylaxis, local and systemic reactogenicity, including immune-complex disease); suicidal ideation (C-SSRS); behavior (NPI); cognitive and functional assessments (RBANS, CDR-SB) to assess safety; vital signs; MRI imaging; electrocardiogram; routine hematology and biochemistry evaluation in blood and urine; evaluation of autoimmune antibodies including anti-dsDNA antibodies in blood; inflammatory markers in blood and CSF.

Immune response (i.e. immunogenicity): Anti-pTau IgG titers in serum (e.g. geometric mean, change from baseline, responder rate, peak and area under the curve).

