# 7.0 Study Endpoints

## 7.1 Primary Endpoints

The primary focus of this study is the assessment of safety and tolerability of ACI-35.030 and JACI-35.054. Safety and tolerability will be assessed by examination of a number of endpoints:

- Adverse events
- Immediate and delayed reactogenicity (e.g. anaphylaxis, local and systemic reactogenicity, including immune-complex disease)
- Suicidal ideation as assessed by Columbia-Suicide Severity Rating Scale (C-SSRS)
- Behavior as assessed by Neuropsychiatric Inventory Scale (NPI)
- Cognitive and functional assessments (RBANS, CDR-SB)
- Vital signs
- Magnetic Resonance Imaging (MRI) imaging
- Electrocardiogram
- Routine hematology and biochemistry evaluation in blood and urine
- Evaluation of autoimmune antibodies including anti-DNA antibodies in blood
- Inflammatory markers in blood and CSF

The immune response (i.e. immunogenicity) will be assessed by:

• Anti-pTau IgG and Anti-ePHF IgG titers in serum (e.g. geometric mean, change from baseline, responder rate, peak and area under the curve)

**Note**: anti-pTau IgG means the antibody response generated against pathological Tau species. This umbrella denomination includes anti-pTau IgG and anti-ePHF IgG responses.

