## 8.8 Treatment Emergent Adverse Event

A treatment emergent adverse event (TEAE) is defined as:

- any AE that has an onset on or after the first dose of investigational product
- or any pre-existing condition that has worsened on or after the first dose of investigational product
- or any AE that starts prior to the end of the designated follow-up period, i.e. 24 weeks (6 months) after the end of the treatment period.

If applicable, the assessment of whether or not an AE is treatment emergent should include both the date and time relative to the first administration of study vaccine.

#### Example 1

Subject	Date of First Injection	AE Start Date	AE Stop Date	TEAE?
100101 NB. AE stopped p	16-Oct-2019 rior to the first administration of	14-Sep-2019 f vaccine, not TEAE.	15-Oct-2019	No
Example 2				
Subject	Date of First Injection	AE Start Date	AE Stop Date	TEAE?
100101 NB. AE started aft	16-Oct-2019 er the first administration of vad	18-Oct-2019 ccine, TEAE.	21-Oct-2019	Yes

Please refer to SAP Section 8.11, below for how to handle partial or missing dates in the assessment of whether or not an event is a TEAE.

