Table 14.2.9.2.1 Anti-CRM IgG (AU/mL) titers, in Serum – Responder Analysis (Per Protocol Population)			Х
Table 14.2.9.3 Anti-CRM IgG (AU/mL) titers, in serum, Peak and Area Under the Curve (Intention-to-Treat Population) *		X 	Х
Table 14.2.9.3.1 Anti-CRM IgG (AU/mL) titers, in Serum, Peak and Area Under the Curve (Per Protocol Population)			Х
Table 14.2.9.4 Key Antibody Ratios, in Serum, and Change from Baseline (Intention-to-Treat Population)			Х
Table 14.2.9.4.1 Key Antibody Ratios, in Serum, and Change from Baseline (Per Protocol Population)			Х
Table 14.2.10.1.1 Summary of Actual Value and Change from Baseline in AD Biomarkers (in Plasma) by Time Point (Intention-to-Treat Population)			х

 Not applicable to Cohort 2 subjects.

 Not applicable to Cohort 1 subjects.

Statistical Analysis Plan

MAIN Statistical Analysis Plan	Cohort 1 Interim Analysis (IA1)	Cohort 1 IA2 to IA7 Cohort 2 IA1 to IA6	Final Analysis
Table 14.2.10.1.1.1 Summary of Actual Value and Change from Baseline in AD Biomarkers (in Plasma) by Time Point (Per Protocol Population)			x
Table 14.2.10.1.2 Summary of Actual Value and Change from Baseline in AD Biomarkers (in CSF) by Time Point (Intention-to-Treat Population)			х
Table 14.2.10.1.2.1 Summary of Actual Value and Change from Baseline in AD Biomarkers (in CSF) by Time Point (Per Protocol Population)			Х
Table 14.2.10.1.2.2 Summary of Actual Value of AD Biomarkers for Eligibility (in CSF) by Time Point (Intention-to-Treat Population)			Х
Table 14.2.10.1.2.3 Summary of Actual Value of AD Biomarkers for Eligibility (in CSF) by Time Point (Per Protocol Population)			Х
Table 14.3.2.1 Overall Summary of Adverse Events and Treatment-Emergent Adverse Events (Safety Population)			Х
Table 14.3.2.2 Treatment-Emergent Adverse Events by System Organ Class and Preferred Term (Safety Population)			Х
Table 14.3.2.3 Serious Treatment-Emergent Adverse Events by System Organ Class and Preferred Term (Safety Population)			Х
Table 14.3.2.4 Severe Treatment-Emergent Adverse Events by System Organ Class and Preferred Term (Safety Population)			Х
Table 14.3.2.5 Adverse Drug Reaction Events by System Organ Class and Preferred Term (Safety Population)   Table 14.3.2.6 Treatment-Emergent Adverse Events Leading to Discontinuation of Study Treatment by System Organ Class and Preferred Term (Safety Population)   Term (Safety Population)			X

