Figure 14.5.3 Individual Value over Time of MRI Volume by Brain Region (Intention-to-Treat Population)			Х
Figure 14.5.4 Box Plot of MRI Volume by Brain Region by Visit and Treatment Group (Intention-to-Treat Population)			Х
Listing 16.1.7 Randomization Assignments (All Randomized Subjects)			Х
Listing 16.2.1.1 End of Study (Intention-to-Treat Population)			Х
Listing 16.2.1.2 End of Investigational Product (IP) Treatment Phase (Intention-to-Treat Population)			Х
Listing 16.2.2.1 Protocol Deviations (Intention-to-Treat Population)			Х
Listing 16.2.2.2 COVID-19 Related Protocol Deviations (Intention-to-Treat Population)			Х
Listing 16.2.3.1 Subject Analysis Sets (All Enrolled Subjects)			Х
Listing 16.2.3.2 Subject Visits (Intention-to-Treat Population)			Х
Listing 16.2.4.1 Demographic and Baseline Data (Intention-to-Treat Population)			Х
Listing 16.2.4.2 Medical History (Intention-to-Treat Population)			Х
Listing 16.2.4.3 Prior and Concomitant Medications (Safety Population)			Х
Listing 16.2.4.4 Prior and Concomitant Procedures (Safety Population)			Х
Listing 16.2.5.1 Administration of Investigational Product (Intention-to-Treat Population)			Х
Listing 16.2.5.2 Treatment Compliance (Intention-to-Treat Population)			Х
Listing 16.2.7.1 Adverse Events (Safety Population)			Х
Listing 16.2.7.2 Serious Treatment-Emergent Adverse Events (Safety Population)			Х
Listing 16.2.7.3 Treatment-Emergent Adverse Events Leading to Discontinuation of Study Treatment (Safety Population)			Х
Listing 16.2.7.4 Treatment-Emergent Adverse Events Leading to Discontinuation from the Study (Safety Population)			Х
Listing 16.2.7.5 Treatment-Emergent Adverse Events with Outcome of Death (Safety Population)			Х
Listing 16.2.7.6.1 Injection Site Reaction Treatment-Emergent Adverse Events (Safety Population)			Х
Listing 16.2.7.6.2 Injection Site Reaction Treatment-Emergent Adverse Events – Sub-components (Safety Population)			Х
Listing 16.2.7.6.3 Presence or Absence of Injection Site Reactions by Visit at the Time of Injection Administration (Safety Population)			Х

[figure not shown]
Statistical Analysis Plan

MAIN Statistical Analysis Plan	Cohort 1 Interim Analysis (IA1)	Cohort 1 IA2 to IA7 Cohort 2 IA1 to IA6	Final Analysis
Listing 16.2.7.7.1 Magnetic Resonance Imaging (MRI) Results (Intention-to-Treat Population)			Х
Listing 16.2.7.7.2 Volumetric Magnetic Resonance Imaging (MRI) Results (Intention-to-Treat Population)			Х

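### Reactogenicity is a named primary safety endpoint, but no planned adverse-event table or figure summarizes local or systemic reactions by injection number or by time since injection

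*SAP*

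**What the plan says.** SAP 7.1 lists as a primary safety endpoint, in its own bullet after adverse events, "Immediate and delayed reactogenicity (e.g. anaphylaxis, local and systemic reactogenicity, including immune-complex disease". Protocol 2.2.1 has the same wording.

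The analysis is in SAP 11.5.1. Beyond an overview table, it states: "Selected TEAE categories from above will also be summarized by MedDRA SOC and PT". Severity, relationship and most-frequent-event tables follow (14.3.2.9 to 14.3.2.11), all by treatment group. The only timing output for adverse events is a chart of time to first SAE, counted from the first injection. The section ends: "All AEs [Non-Injection Site Reactions (ISR) and ISRs] will be listed".

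Injection-site reactions have three dedicated outputs, all listings (16.2.7.6.1 to 16.2.7.6.3). One of them is by injection: "Listing 16.2.7.6.3 Presence or Absence of Injection Site Reactions by Visit at the Time of Injection Administration (Safety Population". The DSMB set in Appendix 2 likewise has an injection-site listing and no table by injection.

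SAP 11.5.3 summarizes vital signs at each dosing visit by hour after the dose, as change from the pre-dose value (Table 14.3.4.1), with a shift table (14.3.4.2). The normal temperature range is 35 to 40 °C.

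The adverse-event window is stated in two ways. SAP 11.5 evaluates the primary adverse-event endpoints through the end of treatment. SAP 8.8 counts as treatment-emergent "any AE that starts prior to the end of the designated follow-up period", that is, up to Week 74.

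**The concern.** The endpoint contains a timing distinction (immediate or delayed) and a site distinction (local or systemic). SAP 11.5.1 defines neither, and gives no onset window and no per-injection denominator. SAP section 12 does not record the endpoint as dropped.

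For a vaccine given four times, one wants to know whether reactions fade or build with later injections, and whether that depends on dose. The protocol gives reason to look: it describes dose-dependent injection-site reactions with the predecessor vaccine (1.5.1), partly justifies the intramuscular route by local tolerability (1.3), and makes the primary endpoints the basis for choosing the vaccine (1.4).

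The data are collected. The injection site is observed at 1, 2, 4, 8, 12 and 24 hours after the first dose and at 1, 2 and 4 hours after later doses, and a call follows 48 to 72 hours after each. At stake is whether this information reaches the report as a summary or only as subject-level lines.

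**Working it through.** **1. The plan's own safety figures.** For 6 active subjects (protocol 5.3.1, SAP 6.1), the chance of seeing at least one event is 1 − (1 − p)^6. This gives 1 − 0.99^6 = 5.9% and 1 − 0.90^6 = 46.9%; the plan states 6% and 47%. The upper bound with no events is 1 − (1 − c)^(1/6): 23.5% at 80% confidence and 31.9% at 90%; the plan states 24% and 32%. All four reproduce. They concern subjects who ever have an event, and say nothing per injection.

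**2. Endpoint against outputs** (SAP 11.5.1, 11.5.3 and Appendix 2 titles).
- *Local reactions:* Appendix 2 calls them TEAEs ("Listing 16.2.7.6.1 Injection Site Reaction Treatment-Emergent Adverse Events (Safety Population"), and nothing excludes them from "Table 14.3.2.2 Treatment-Emergent Adverse Events by System Organ Class and Preferred Term (Safety Population" or from the severity, relationship and most-frequent tables. They therefore get a pooled count and percentage, but no count per injection.
- *Systemic reactions:* these fall in the same pooled tables and are not identified as reactions to an injection.
- *Immediate versus delayed:* no adverse-event table or figure uses time since injection.
- *By dosing visit and post-dose hour:* vital signs only.

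**3. What a pooled row hides.** In a group of 6, suppose five subjects react once each. If all five react at injection 1, the row reads 5/6 = 83%, 5 events. If all five react at injection 4, it reads the same.

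The same holds for rates. With independent injections the ever-reacted rate is 1 − Π(1 − p_j):
- 20% at every injection: 1 − 0.8^4 = 59%
- rising 10, 15, 20, 33%: 1 − 0.90 × 0.85 × 0.80 × 0.67 = 59%
- falling 33, 20, 15, 10%: the same product, 59%

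**4. Unequal exposure.** The third injection was not given to 7 of 8 sub-cohort 1.1 subjects (SAP 6.0). If the one exception was on active vaccine, the six active subjects were due 5 × 3 + 4 = 19 injections. If that subject was on placebo, they were due 6 × 3 = 18. The plan was 24.

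The documents give no per-injection reaction rate, so p is assumed, with independence between injections:

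| Assumed p | 3 injections: 1 − (1 − p)^3 | 4 injections: 1 − (1 − p)^4 | Gap, points |
|---|---|---|---|
| 10% | 27.1% | 34.4% | 7.3 |
| 20% | 48.8% | 59.0% | 10.2 |
| 30% | 65.7% | 76.0% | 10.3 |

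If the exception was an active subject, the group gap is five-sixths of this (at 20%: 5/6 × 10.2 = 8.5). If the same subjects react every time, the rate is p in both columns and the gap is zero.

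**5. Precision of the missing table.** Exact 95% intervals are 4% to 78% for 2/6, and 6% to 48% for 4/18. Eighteen is the planned active number in a fully expanded sub-cohort (6 + 12). Sub-cohort 1.2 enrolled 25 subjects in all; the arm of the extra subject is not stated.

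**The case against.** The SAP implements the analysis section of the protocol. Protocol 5.3.5 and 5.3.5.2 describe primary safety through the type, frequency and intensity of adverse events and ask for no per-injection table. Local reactions do get a count, percentage, severity and relatedness by dose group, and anaphylaxis reported as an adverse event would have its own preferred-term row. SAP 11.5.2 promises by-visit summaries of continuous laboratory parameters, a list that includes CRP and complement. Visits 2, 4, 6 and 9 fall about two weeks after injections 1 to 4, so these results bear on systemic inflammation and immune-complex disease. In groups of 6 a reader can count from Listing 16.2.7.6.3. Table 14.1.6 discloses how many subjects received each injection. The analysis is descriptive, no decision rule uses the missing table, and the DSMB sees unblinded safety data quarterly.

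Much of this stands, and it limits the point. A reader might infer that injection-site reactions are only listed, or that the endpoint has no summary at all. The documents do not support either reading, given the pooled TEAE tables and the vital-signs tables. A reader might also infer that the 300 µg group will look better tolerated by about 10 points. That figure rests on assumed rates and independence. In a group of 6 it is 0.6 of a subject, and it would largely vanish if nearly everyone reacts, as the protocol reports for the highest doses of the predecessor vaccine.

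What the objection does not answer is the immediate/delayed split. The plan names it, and no adverse-event summary shows it. Vital signs are a weak substitute, because a temperature up to 40 °C is not flagged and other systemic symptoms are not covered. Small groups are a reason to print n/N, not to omit the row; the SAP already tabulates vital signs by visit and hour in groups of the same size.

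**Conclusion.** The point holds as a should-fix. The planned adverse-event outputs cannot report part of a named primary safety endpoint: the immediate/delayed split and the course of reactions over injections. Identical pooled rows can come from waning or from growing reactions, which needs no assumed rate to show. The effect of the missed third injection does need assumptions: 7 to 10 points in favour of 300 µg at per-injection risks of 10% to 30% with independent injections, down to zero with full dependence within subjects.

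The conclusion about missing outputs rests on SAP 11.5.1 and the output titles in Appendix 2. The table shells are a separate document that was not available, so a split inside a shell cannot be ruled out. A more severe grading is not supported: the analysis is descriptive, the underlying records are listed, and safety oversight does not depend on this table.

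**What to change.** Add to SAP 11.5.1 and Appendix 2 a descriptive table by treatment group, with pooled placebo (protocol 5.3.4 allows pooling), and by injection 1 to 4. The denominator is the subjects who received that injection. Show n/N (%) by maximum severity for:
- any injection-site reaction;
- any systemic adverse reaction, defined as a TEAE other than an injection-site reaction, and shown again restricted to possibly or probably related events.

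Split each by onset: within the observation period and 48-72 hour call window, or later but before the next injection (end of follow-up after injection 4). Add whole-study rows for anaphylaxis and for immune-complex-type events.

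Two points belong in the footnotes. Number injections by planned visit, so that the Week 48 dose in sub-cohort 1.1 stays injection 4. The intervals that contain the later windows also differ in length: 8, 16 and 24 weeks between injections and 26 weeks after the last (Weeks 0, 8, 24, 48, 74), or 48 − 8 = 40 weeks after injection 2 where injection 3 was missed. Later-onset counts are therefore not directly comparable across rows.

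Reconcile the adverse-event window between SAP 11.5 (end of treatment) and SAP 8.8 (end of follow-up).

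The cost is one or two shells and an updated SAP, which SAP 3.0 requires the sponsor to approve again. No new data are needed: onset dates, injection dates and injection-site records are already planned for listing. The percentages will be imprecise in groups of 6.
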